Effects of the ingestion of human, cow and cow-modified milk, on glucose, amino acid and hormone responses in humans

Acronym: PROLAT (extract)

Objects of the study:

To evaluate the effects of the ingestion of human and cow milk, as well as of protein-modified cow milk, on glucose, amino acid and hormone responses (insulin, glucagon, IGF-1, incretins) in humans.

Background

Milk is the first food for the development of the neonate [...] and a key nutritional substrate also over the entire human life [...]. The nutritional importance of milk (1-5) is due to its balanced content in both essential and non essential nutrients, such as:

- High biological value proteins, rich in essential amino acids;
- Lipids
- Lactose
- Minerals
- Vitamins
- Energy

Furthermore, milk provides probiotics and other functional substances [...] and is a key stimulator of hormone secretion favoring nutrients' utilization.

[...], Among the stimulated hormones, the most important ones are insulin, glucagon, IGF-1, and the incretins GLP-1 and GIP (1). Milk lactose and proteins have a key role in the stimulation of their secretion [...] (2, 3). Human milk, despite its low protein content, exhibits a powerful effect on insulin secretion (4) [...].

Species-specific differences in milk composition.

Milk from various species besides the human one, can be used in human nutrition, cow, sheep, goat and donkey milk [...].

There are important species-specific differences in milk [...]. For instance human milk, as compared to cow milk, is moderately hypercaloric, hyperglucidic, markedly ipoproteic, isolipidic, richer in iron and relatively poorer in salts and oligoelements (4).

The qualitative composition of the protein fraction is also different between human and cow milk [...]. The effects of such a different protein composition on hormone secretion is not known.

[...]

Human milk apparently is endowed with specific effects on hormone secretion [...]. The factors underlying such effect are not yet known (5).

The aims of the study are therefore the following:

1. To determine glucose, amino acid, and hormonal responses to natural human and cow milk at strictly-controlled, iso-lactose and iso-volume conditions.
2. To determine the same responses to either human or cow milk at modified protein concentrations. [...].

Experimental design:

- Recruitment of healthy volunteers of both sexes (age between 20 and 60 yrs, BMI between 18.5 e 25 Kg/m²),
- A written consent form will be signed.
- The milk load(s) will be administered after the overnight fast.
- At least one week will be allowed between each test in the same volunteer.

The following milk type will be randomly administered to the volunteers:

1. Human natural milk
2. Cow natural milk
3. A low-protein, cow-derived milk, similar to the human one for total protein content, but with a casein-to-whey protein ratio of casein typical of human milk (20:80);
4. A high-protein, cow-derived milk, similar to natural cow milk for total protein content, but with a casein-to-whey protein ratio of casein typical of human milk (20:80);

All milk loads will contain the same lactose amount (0.36 g/kg BW)

The human milk, whenever available, will be furnished by the Milk bank of the Dept. of Pediatrics of Padova University Hospital or by other available official Milk banks [...].

All modified milk types will be handled and prepared under proper aseptic conditions.

Study protocol (see also the attached scheme)

The volunteers were admitted to the clinical study unit at 08:00 after the overnight fast. A 20-g cannula was inserted in an antecubital vein for blood withdrawal. After two baseline samples spaced by \approx 10', the milk load was administered over 2'-5' to the volunteers. Starting from the end of milk ingestion ($t = 0'$), blood samples were taken at min 5', 10', 20', 30', 60', 90', 120', 180', and 240', then immediately transferred to two series of plastic tubes, containing either Na-EDTA (6% w/vol), for glucose, amino acid, insulin and C-peptide determinations, or a protease inhibitor (EMD Millipore Corporation, Merck KGaA, Darmstadt, Germany), for GIP and GLP-1 assay [...]

Key References:

2. Hartmann R and Meisel H. Food-derived peptides with biological activity: from research to food applications. *Current Opinion in Biotechnology* 2007, 18:163–169.

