Effects of the ingestion of human, cow and modified cow milk, on glucose, amino acid and hormone responses in humans

Acronym: PROLAT

Statistical analysis

The statistical analysis was performed either on data absolute values, or as relative changes vs baseline. The incremental area(s) under the curve (iAUC) within specific time intervals were calculated using the trapezoidal approach. The one Way ANOVA was applied to analyze one single set of data in the four experimental groups, followed by post-hoc analysis using the Fisher's test. With multiple measurements over time, the data were analyzed using the two-Way Analysis of Variance (ANOVA) for repeated measurements, followed by the post-hoc Fisher's test. The two tailed Student's t test for unpaired data was used in some instances for head-to-head comparisons, as specifically indicated. The Statistica® Software (version 10) program was employed. A p value equal or less than 0.05 was considered statistically significant. Power analysis, sufficient to detect a ≈30% difference between two means, with a RMSSE (Root Mean Standardized Square Error) of <0.5, a power of 80%, and a two-sided level of significance of 0.05%, indicated a sample size of at least 29 subjects.

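### The SAP ties no milk comparison to an aim, does not separate one-factor pairs from mixed pairs, and uses unpaired Fisher testing with about 12% any-error per outcome when one milk differs

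*Protocol*

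**What the plan says.** Under Experimental design the Protocol lists four loads: "Human natural milk", "Cow natural milk", "A low-protein, cow-derived milk, similar to the human one for total protein content", and "A high-protein, cow-derived milk, similar to natural cow milk for total protein content". Both modified milks have a 20:80 casein:whey ratio, described as the human one. Lactose is equal in all four. At least a week separates tests on one volunteer.

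Aim 1 concerns responses to the two natural milks. Aim 2 concerns the same responses when the protein level of human or cow milk is altered; text after Aim 2 is omitted from this extract. The Background says that "The qualitative composition of the protein fraction is also different between human and cow milk" and that the hormonal effect of this difference is unknown.

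On analysis, the SAP states: "The one Way ANOVA was applied to analyze one single set of data in the four experimental groups". Fisher's post-hoc test follows. Series over time get a two-way repeated-measures ANOVA, also followed by Fisher's test. Unpaired t tests serve for some head-to-head comparisons, which the SAP does not name. The test level is 0.05. No pair is listed, no comparison is assigned to an aim, and no further multiplicity control is given.

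**The concern.** The modified milks are each matched to a natural milk on total protein and share one ratio. That construction lets some pairs speak to protein amount alone, ratio alone, or source at matched amount and ratio. The SAP makes no use of it. High- v low-protein modified milk (amount alone) has the same standing as natural cow v low-protein modified milk (amount and ratio together), so a significant result from the second could be reported as a protein-amount effect and the plan would not prevent it.

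Two features of the method add to this. Fisher's test after an F test does not control the chance of a false claim among four milks once one of them differs. And a one-way ANOVA or unpaired t test treats repeat tests on one volunteer as independent, so it leaves between-volunteer variation in the error term.

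**Working it through.** **Coding the milks** (Protocol, Background and Experimental design). The cow ratio is never given as a number. Coding it as different from 20:80 rests on the Background statement quoted above and on the fact that the high-protein modified milk is set apart from natural cow milk by its ratio.

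| Milk | Source | Amount | Ratio |
|---|---|---|---|
| H, human | human | low | 20:80 |
| C, natural cow | cow | high | cow |
| L, low-protein modified | cow | low | 20:80 |
| M, high-protein modified | cow | high | 20:80 |

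**Factors changed per pair**

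| Pair | Changes | Role |
|---|---|---|
| H v C | source, amount, ratio | Aim 1 itself |
| M v L | amount | one factor |
| C v M | ratio | one factor |
| H v L | source | one factor |
| H v M | source, amount | mixed |
| C v L | amount, ratio | mixed |

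The one-factor contrasts add up to the Aim 1 difference: H − C = (H − L) + (L − M) + (M − C).

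**What cannot be estimated.** Four means support an intercept and three main effects (design rank 4). The cow ratio occurs only with high protein, so an amount-by-ratio column duplicates the ratio column and the rank stays at 4. The ratio effect is available only at high protein, and the amount effect only at 20:80.

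**The SAP's own figure.** The minimum of 29 participants cannot be reproduced, because RMSSE is only bounded (below 0.5) and no SD is given. For orientation, RMSSE of exactly 0.5 at level 0.05 and 80% power, with noncentrality n(k − 1)RMSSE², needs 16 per group for four groups and 33 per group for two. Nor does the SAP say whether 29 is a total or a number per milk. Below, 29 per milk is an assumption; the structural point does not depend on it.

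**Error rate of Fisher's test after a significant F** (simulation, 29 independent values per milk, one outcome, all pairs tested):

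- All four milks equal: about 5%.
- One milk far from three equal ones: about 12%. The F test then nearly always passes, leaving three true-null pairs at 0.05 each. If independent, that would be 1 − 0.95³ = 14.3%; shared means lower it.
- The shift need not be extreme: 9.9% at 0.5 SD and 11.9% at 1 SD. A within-subject ANOVA gives 10.0% and 12.1%, so pairing alone does not cure this.
- Milks split two and two: about 10% (1 − 0.95² = 9.75%).

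**Error rate of planned contrasts** (H v C, C v M, M v L, H v L):

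- H v C at 0.05 on its own, with Holm over the other three: 8.5 to 9% when all milks are equal or one modified milk differs.
- One Holm family of four (first step 0.05/4 = 0.0125): at or below 5%, as Holm's bound requires.

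**Power at an assumed 0.8 SD, 29 per milk.** The standardised difference is 0.8 × √(29/2) = 3.046.

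- Unadjusted: Φ(3.046 − 1.960) = 0.86. The F requirement brings this to about 0.81 in simulation.
- At 0.0125: Φ(3.046 − 2.498) = 0.71.
- Pairing changes the variance of a difference from 2σ² to 2σ²(1 − ρ). Returning to 0.81 needs 3.046/√(1 − ρ) = 2.498 + 0.878 = 3.376, so ρ of about 0.19, if volunteers take both milks.

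**The case against.** A reader might infer that Aim 2 cannot be answered from the planned tests, or that half of the six pairs are invalid. The documents do not support either. If Fisher's test covers all pairs, as is usual, the three one-factor pairs are among the tests. Human v natural cow milk is Aim 1, a comparison of whole milks, so its mixture of factors is the question asked. That leaves two mixed pairs, and nothing says that either will be read as a single-factor effect.

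Nor does any stated aim promise a factorial or an interaction. Separating amount from ratio is an inference from the Background and from how the milks are matched, and the Protocol is an extract with text missing after Aim 2. All-pairs testing is itself inferred, since the SAP lists none and says that some comparisons were selected.

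The source contrast is also not pure. The Background calls human milk "moderately hypercaloric, hyperglucidic, markedly ipoproteic, isolipidic, richer in iron and relatively poorer in salts and oligoelements" relative to cow milk, and the extract does not say whether the modified milks are matched to it on energy or minerals.

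Finally, the documents never say that each volunteer takes all four milks. Human milk is given subject to availability, and the SAP speaks of groups.

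All of this stands and limits the claim. It does not supply the missing link from comparison to aim, does not remove the 12%, and does not justify unpaired tests where a volunteer was tested more than once.

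**Conclusion.** The point holds in limited form. Aim 2 is partly answerable: amount at 20:80, ratio at high protein, and a source contrast that bundles minerals and possibly other components. The contrasts that answer it are not prespecified or set apart from the two mixed pairs (human v high-protein modified; natural cow v low-protein modified). Aim 2 also mentions human milk, yet both modified milks are cow-derived.

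Any-error is about 12% per outcome when one milk differs and about 10% in a two-two split, against a nominal 5%. This assumes 29 per milk, all pairs tested, and Fisher's test used only after a significant F. Without that condition, testing all six pairs gives about 20% when no milk differs. These rates are for one outcome; the number of outcomes is a separate matter.

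The absent low-protein milk at the cow ratio is a limit to state. It does not show that the design fails its aims or that a fifth milk is required. The change is worth making because it improves the method at the cost of SAP text.

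**What to change.** For each outcome, replace the one-way ANOVA, the Fisher tests and the unpaired t tests with a model that has milk as a fixed effect and volunteer as a random effect. For series over time, apply it to the chosen summary or add time to the model. It can include volunteers who did not take every milk. Prespecify four contrasts:

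- Aim 1: human v natural cow.
- Aim 2, ratio: natural cow v high-protein modified.
- Aim 2, amount: high- v low-protein modified.
- Aim 2, source: human v low-protein modified.

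Apply one Holm adjustment over all four. Do not leave Aim 1 outside the family, which lets any-error rise to about 9%. Report the two mixed pairs descriptively. State that the ratio effect is estimated only at high protein, the amount effect only at 20:80, and that an amount-by-ratio interaction cannot be estimated.

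Cost: SAP wording, with no new milk, visit or volunteer. Two pairs lose formal testing. Each contrast loses about 10 points of power against Fisher's test (about 0.81 to 0.71 at the assumed 0.8 SD and 29 per milk), offset to the extent that responses within a volunteer are correlated. If few volunteers took more than one milk, that offset is small.

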Effects of the ingestion of human, cow and modified cow milk, on glucose, amino acid and hormone responses in humans

Acronym: PROLAT

Statistical analysis

The statistical analysis was performed either on data absolute values, or as relative changes vs baseline. The incremental area(s) under the curve (iAUC) within specific time intervals were calculated using the trapezoidal approach. The one Way ANOVA was applied to analyze one single set of data in the four experimental groups, followed by post-hoc analysis using the Fisher's test. With multiple measurements over time, the data were analyzed using the two-Way Analysis of Variance (ANOVA) for repeated measurements, followed by the post-hoc Fisher's test. The two tailed Student's t test for unpaired data was used in some instances for head-to-head comparisons, as specifically indicated. The Statistica® Software (version 10) program was employed. A p value equal or less than 0.05 was considered statistically significant. Power analysis, sufficient to detect a ≈30% difference between two means, with a RMSSE (Root Mean Standardized Square Error) of <0.5, a power of 80%, and a two-sided level of significance of 0.05%, indicated a sample size of at least 29 subjects.

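### The SAP allows testing on absolute values or on relative change from baseline with no rule for which counts, and never adjusts for the baseline collected at each test: state one scale per measure and use that baseline as covariate

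*SAP*

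**What the plan says.** The SAP is one paragraph, *Statistical analysis*. On scale it says "The statistical analysis was performed either on data absolute values, or as relative changes vs baseline". It adds a third measure: "The incremental area(s) under the curve (iAUC) within specific time intervals were calculated using the trapezoidal approach". It does not say which intervals, or whether areas below baseline are subtracted (net iAUC) or dropped.

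The tests are then listed. For single data sets, "The one Way ANOVA was applied to analyze one single set of data in the four experimental groups"; for serial measurements, "the data were analyzed using the two-Way Analysis of Variance (ANOVA) for repeated measurements"; both are followed by Fisher comparisons. Unpaired t tests are used for some head-to-head comparisons. The remark that uses are indicated where they occur applies only to those t tests. No test has a baseline covariate. The decision rule is "A p value equal or less than 0.05 was considered statistically significant".

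The protocol, under *Study protocol*, has the baseline data: "After two baseline samples spaced by" about ten minutes, the milk is given. Under *Experimental design* it expects repeat testing: "At least one week will be allowed between each test in the same volunteer". The protocol extract has no analysis section that assigns a scale.

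**The concern.** Two scales are open for every analyte, and nothing says which result stands if they disagree. A 0.05 rule holds its nominal rate only when a single test supplies the p-value. If the analyst may look at both and report the significant one, the rate rises.

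The second issue is what each scale does with the fasting level. One-way ANOVA or an unpaired t test on absolute values ignores it. Relative change and iAUC divide by it or subtract it, in effect fixing its coefficient in advance. When fasting and post-load values are weakly correlated, this adds noise and loses power. Estimating the coefficient, with baseline as covariate, avoids that loss and uses data already collected.

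**Working it through.** **Inputs.** From the documents: the two scales, the 0.05 rule, four milks, two baseline samples, and 29 as a size (the SAP does not say whether per milk or in total). The documents give no SD, CV or correlation, so those below are assumed. Ranges and medians describe a grid of settings and are not probabilities.

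**1. Limits by arithmetic.** For two tests at 5% each, P(either) = 5% + 5% − P(both). This is 5% if they always agree and 10% if they are never significant together. Independent tests would give 1 − 0.95² = 9.75%.

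**2. Where the rate falls.** Null log-normal data were simulated, 20,000 sets in each of 36 settings: fasting CV 10, 20, 30 or 40%; post-load CV 20, 40 or 60%; correlation 0, 0.2 or 0.5; 15 or 29 per group; paired and unpaired two-sided t tests.

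| Rule | False positives |
|---|---|
| One scale, no covariate (the SAP's nominal 5%) | 4.2–5.3% |
| Smaller p of absolute value and ratio | 5.1–10.0%, median about 7.4% |
| Same, fasting CV 10% only | 5.1–7.7% |
| Smaller p of absolute value and difference (unpaired; post-load median 1.5 times fasting) | median about 6.5% |
| Same, fasting CV 10% only (15 per group) | 5.2–6.6% |

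Percent change is the ratio minus 1, times 100, so it gives the same test as the ratio.

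**3. Is the covariate enough without a stated scale?** No. In the unpaired data, with both versions baseline-adjusted, choosing between raw value and raw ratio gives 4.9–8.6% (median 6.0%), and choosing between raw and log value gives 5.3–6.7% (median 5.9%). One stated scale with the covariate gives 4.4–5.3%.

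**4. When the covariate makes the choice irrelevant.** If log y − log b = milk + β·log b, then log y = milk + (β + 1)·log b: same milk difference, same p. Likewise net iAUC = AUC − T·b, with T the length of the interval, so AUC and net iAUC agree once the same b is a covariate. Neither identity covers raw value against raw ratio, or positive-only iAUC.

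**5. Power.** Let r be the within-volunteer correlation of fasting and post-load log values, and k the fasting log-SD divided by the post-load log-SD. Error variance relative to absolute values is

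- covariate: 1 − r²
- log ratio: 1 + k² − 2rk, which exceeds the covariate's by (k − r)².

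Example, k = 1 and r = 0.2: the log ratio gives 1 + 1 − 0.4 = 1.6. At 80% power the standardised effect is 1.96 + 0.84 = 2.80; 2.80/√1.6 = 2.21, and Φ(2.21 − 1.96) is about 60%. Simulation gives 61%.

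Simulated power (%), two-milk contrast, with the effect set for 80% on absolute values in the same design and a fixed volunteer effect in both models:

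| Analysis and design | r = 0 | 0.1 | 0.2 | 0.3 | 0.5 |
|---|---|---|---|---|---|
| Covariate, 29 volunteers × 4 milks | 79.3 | 79.9 | 81.0 | 82.9 | 89.5 |
| Covariate, 15 × 4 milks | 78.7 | 79.3 | 80.3 | 82.5 | 89.3 |
| Covariate, 29 × 2 milks | 78.2 | 78.4 | 79.6 | 82.3 | 88.4 |
| Covariate, 15 with 1 to 4 milks | 77.2 | 78.5 | 78.9 | 80.6 | 88.1 |
| Log ratio, 29 × 4, k = 0.5 | 71 | 74 | 78 | 82 | 90 |
| Log ratio, 29 × 4, k = 1 | 51 | 55 | 61 | 66 | 80 |

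With separate groups of 29 per milk and no volunteer effect, the covariate gives 80.0, 80.4, 81.6, 83.6 and 89.9.

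The worst cost against absolute values is 80 − 78.7 = 1.3 points when all take four milks, and 80 − 77.2 = 2.8 points in the smallest partial-overlap design.

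**The case against.** - **The covariate is not what controls error.** This stands. One stated scale without it already gives 4.2–5.3%. Naming absolute values would also avoid the loss from dividing by baseline, so the largest gap (79 against 51 at r = 0) argues against the ratio more than for the covariate. The gain over absolute values depends on r, which neither document gives. What remains is that the covariate is cheap, uses samples already drawn, and protects against a poor fixed coefficient whichever scale is chosen.
- **The power benchmark is not the SAP's model.** This stands in part. Most rows include a volunteer effect, whereas the SAP names one-way ANOVA and an unpaired t test. The separate-groups figures, closest to those tests, show the same pattern.
- **Baseline is not wholly ignored.** This is true. Relative change and iAUC use it, and if baseline is a time level in the repeated-measures ANOVA, the milk-by-time interaction tests differential change. The SAP does not say whether it is. None of these estimates a baseline coefficient or says which analysis counts.
- **The inflation depends on the reading and the inputs.** This is also true. It is smaller if relative change is a difference, and the highest rates need a fasting CV of 40% with a post-load CV of 20%, which means more variation before the load than after it.
- **A reader might infer that results were selected by scale.** The documents do not support that. They leave the choice open and report no results.

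**Conclusion.** The point holds as a gap in the plan. The SAP fixes no scale and makes no use of the per-test baseline as covariate. Letting either scale count puts the per-comparison false-positive rate at about 5% to 10%, with a median of about 7.4% (ratio) or 6.5% (difference). One stated scale returns it to about 5%.

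The covariate's benefit is conditional. Against the log ratio it gains up to 28 points when r is 0 and the log-SDs are equal, and essentially nothing when r = k. Against absolute values it is about neutral for r up to 0.2, about 1 to 3 points better at 0.3 and 8 to 10 better at 0.5. It would be too strong to say that the covariate always gains power, or that it cures the choice of scale by itself.

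All sizes rest on assumed CVs and correlations. The sample size of 29 plays no part except as a convenient n. Multiplicity across analytes and milk pairs is separate and is not addressed here.

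**What to change.** In the SAP:

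1. Replace the open choice by one scale, raw or log, for each analyte and measure, fixed without sight of the milk comparison. Net iAUC stays raw because it can be negative.
2. Say whether relative change is a ratio or a difference, and whether iAUC is net.
3. Compare milks on that scale with the mean of that test's two baseline samples as covariate, logged when the outcome is logged.
4. Where volunteers take more than one milk, include a volunteer effect and consider a period term. Make the effect random if some take only one milk; a fixed effect discards their data. In a check with 15 volunteers taking 1 to 4 milks (assumed intraclass correlation 0.3 to 0.7, variances treated as known), the fixed effect raised the contrast variance by a median of 6–14%.
5. Use the same scale in the repeated-measures ANOVA, and say whether baseline is a time level there.
6. Report the other scale as supportive.
7. The SAP and parts of the protocol are in the past tense ("The volunteers were admitted to the clinical study unit at 08:00 after the overnight fast"). If results are already known, say so and label the choice post hoc; new wording cannot make it prespecified.

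The cost is SAP wording, a refit and one degree of freedom, with no new data. If r is near 0, that is about 1 point of power when all volunteers take four milks and up to about 3 points in small partial-overlap designs. Those costs were computed with a fixed volunteer effect; power with a random effect was not simulated.

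### Fisher's LSD does not control family-wise error over four milks (5–12% per single outcome, by pattern), and one-way ANOVA and unpaired t tests ignore the repeat tests the protocol foresees

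*SAP*

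**What the plan says.** The SAP's only section, Statistical analysis, describes three routes to a milk comparison.

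- Single-measure outcomes: a one-way ANOVA "in the four experimental groups, followed by post-hoc analysis using the Fisher's test".
- Time courses: a "two-Way Analysis of Variance (ANOVA) for repeated measurements, followed by the post-hoc Fisher's test".
- Selected contrasts: "The two tailed Student's t test for unpaired data was used in some instances for head-to-head comparisons".

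One threshold serves all three: "A p value equal or less than 0.05 was considered statistically significant". The section names no multiplicity adjustment, primary outcome, limited list of contrasts or sphericity correction.

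On design, the protocol (Experimental design) says "The following milk type will be randomly administered to the volunteers" and lists four milks. It adds: "At least one week will be allowed between each test in the same volunteer". So it foresees more than one milk per volunteer. Neither document says how many each volunteer took, or whether volunteer enters the models for single measures.

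**The concern.** Two features of the analysis interact.

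First, LSD after a significant F test protects the whole set of pairwise comparisons for three groups only. With four, one real difference can make the F test significant, and the milks that are truly equal are then compared at an unadjusted 5% per pair. The milk design makes such a pattern possible. One modified milk is "A low-protein, cow-derived milk, similar to the human one for total protein content" and the other is "A high-protein, cow-derived milk, similar to natural cow milk for total protein content". If total protein alone drove an outcome, there would be two equal pairs.

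Second, a one-way ANOVA and an unpaired t test treat the milks as separate groups of people. If volunteers took several milks and responses are positively correlated within a volunteer, these tests use too large a standard error. Error per comparison falls below 5% and real differences are missed.

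The two faults push in opposite directions. Depending on the pairing, nominal p-values for single outcomes may be too liberal as a set or too conservative, and the public text does not let a reader tell which.

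**Working it through.** The SAP states no family-wise error figure, so there is none to reproduce. Only its sample size enters, as a range.

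**Inputs from the documents.** Four milks, hence 4 × 3 / 2 = 6 pairs. Threshold 0.05 per test. At least 29 subjects, without saying whether in total or per milk, so about 7 (29/4 = 7.25) to 29 per milk. Nine post-dose sampling times.

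**Assumptions.** Fisher's test means LSD; normal data with equal variances; between-milk correlation ρ within volunteer of 0.3, 0.5 or 0.7; 30-minute autocorrelation of 0.5 to 0.9.

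**Step 1: independent groups, or pairing modelled, one outcome.** With real differences large enough for the F test to be significant:

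- One equal pair: 5%.
- Two equal pairs: 1 − 0.95² = 9.75%.
- Three equal: P(Q(3, df) > √2 × t(0.975, df)), where Q is the studentized range. At 7 per milk (df 24), √2 × 2.064 = 2.919 gives 11.9%. At 29 per milk (df 112), √2 × 1.981 = 2.802 gives 12.2%.
- All four equal: 5% if a significant F is required. If not, P(Q(4, df) > same value) = 19.4% and 20.1%.

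Simulation with 7 to 29 per milk, independent or within volunteer, agrees: 9.4–10.0% (two equal pairs) and 11.8–12.4% (three equal). With moderate differences and 15 per milk, the figures are 8.3% / 10.1% when the F test has 50% power and 9.5% / 11.8% at 80%.

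**Step 2: every volunteer on all four milks, pairing ignored.** The true standard error of a difference is σ√(2(1−ρ)/n), but the test uses σ√(2/n). The effective threshold is therefore about 1.96/√(1−ρ).

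| ρ | threshold | per pair | two equal pairs / three equal | simulated, n = 7–29 |
|---|---|---|---|---|
| 0.3 | 2.34 | 1.9% | 3.8% / 5.0% | 4.1–4.5% / 5.1–5.8% |
| 0.5 | 2.77 | 0.56% | 1.1% / 1.5% | 1.4–2.0% / 1.8–2.7% |
| 0.7 | 3.58 | 0.03% | 0.07% / 0.10% | 0.1–0.6% / 0.2–0.8% |

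If thirty volunteers each took only two of the four milks, the fall is smaller: 7.6% / 9.6%, 6.3% / 7.8% and 5.1% / 6.6%.

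**Step 3: power lost.** Take n = 15 and an effect that within-volunteer LSD detects with 80% power, with no F test required. Ignoring pairing gives 68%, 52% and 25% at ρ = 0.3, 0.5 and 0.7. Tukey added to that unpaired analysis gives 39%, 22% and 6%.

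**Step 4: replacement procedures, 29 volunteers, within-volunteer df 84.**

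- Fisher–Hayter: critical value 3.374/√2 = 2.386, or 1.93% per pair. Three equal 5.0%; two equal pairs 1 − 0.9807² = 3.8%.
- Tukey: 3.707/√2 = 2.621, or 1.04% per pair. Three equal 2.8%; two equal pairs 1 − 0.9896² = 2.1%.
- Detectable difference at 80% power relative to LSD, (c + 0.842)/(1.989 + 0.842): Tukey 3.463/2.831 = 1.22; Holm's strictest step of four (c = 2.553) 3.395/2.831 = 1.20; Fisher–Hayter 3.228/2.831 = 1.14. At n = 15 (df 42), Tukey is 1.23 and Holm 1.21.

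These ratios leave out the F test. If LSD also needs a significant F, its power for the Step 3 effect is 61–78% by pattern of means, not 80%. Fisher–Hayter has 59–67% and Tukey 58%.

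**Step 5: time courses, illustrative only.** If all nine times are compared by LSD, family error is 31–59% with independent groups or modelled pairing. With pairing ignored it is 15–32%, 7–15% and 1–3% at ρ = 0.3, 0.5 and 0.7. An uncorrected milk-by-time F test has size 10–16%.

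**The case against.** The strongest reply has four parts.

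**Nothing promised is broken.** The documents name no primary outcome and claim no family-wise 5%. Aim 1 contains a single contrast, human against natural cow milk, which keeps about 5% by itself. In exploratory physiology, unadjusted comparisons at a stated threshold can be defended if labelled. This stands, and it limits the weight of the point.

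**The inflated patterns are not singled out by the design.** Both modified milks have the casein-to-whey ratio typical of human milk (20:80), so the high-protein one differs from natural cow milk in composition even though total protein is matched. The protocol's Background says the hormonal effect of that difference is unknown. Only low-protein modified and human milk match on both protein content and ratio. If that is the sole equal pair, error is 5%. This stands: two equal pairs are possible, not expected, and nothing particular supports the 12% pattern.

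**Pairing may be ignored.** Repeat tests alongside a one-way ANOVA and unpaired t tests make that a live reading, and single-outcome error is then low. True, but the cost moves to power, and time-by-time comparisons can still exceed 5%.

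**The public texts are an extract and one paragraph.** An adjustment or sphericity correction may exist elsewhere. That cannot be excluded. The tests that are named are still the ones described here.

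**Conclusion.** The point holds in a limited form and should be acted on. For one outcome, with independent groups or modelled pairing, LSD after a significant F test has family error of about 5% (all equal, or one equal pair), up to about 10% (two equal pairs) and up to about 12% (three equal), or about 8–10% for the last two patterns if the F test has only moderate power. If the F test is not required, error is about 20% when all are equal. If all volunteers took all four milks and the tests ignore it, error for the two-pair and three-equal patterns is about 4–6% at correlation 0.3 and below 3% at 0.5 or more, with loss of power.

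A reader might infer more than the documents support:

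- That error is 10–12% whenever some milks differ. It is 5% with only one equal pair.
- That the reported tests are simply too liberal. The pairing is not stated, so the direction is open.
- That ignoring repeats makes everything conservative. Time-by-time comparisons may not be, nor the case where volunteers took only some of the milks.
- That time-course error is 31–59%. This rests on assumed autocorrelation and on comparing all nine times, which the SAP does not say was done.

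The LSD reading, the correlations and the group sizes are assumptions.

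**What to change.** In this order:

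1. Where a volunteer took more than one milk, analyse every outcome, including iAUC and the head-to-head comparisons, with volunteer in the model (random effect or within-volunteer ANOVA) and with paired rather than unpaired tests.
2. Within that model, replace LSD by a procedure valid for four milks. Fisher–Hayter stays closest to the present plan because it keeps the ANOVA step. Tukey, or Holm over a short list of contrasts, would also do; label the list post hoc if it was chosen after seeing data. Do not add Tukey to an analysis that ignores pairing.
3. For time-course F tests, use a sphericity correction or a mixed model, and treat single-time-point comparisons as descriptive. In simulation Greenhouse–Geisser held 4.6–5.4% with milks between volunteers, but fell to 0.5–3.7% with milk and time both within volunteer. A mixed model may suit that case better, though its size at these numbers was not checked.

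The cost is re-analysis of existing data (the SAP is written in the past tense) and the loss of some nominally significant differences. The detectable difference grows by about 20–23% with Holm's strictest step or Tukey, measured against LSD without an F test in the same model, and by less against LSD with one. If the present analysis ignores pairing and all volunteers took all four milks, pairing plus Tukey changes the detectable difference by +8 to +9% at correlation 0.3, −4 to −5% at 0.5 and −22% at 0.7.
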